6.0 ANALYSIS POPULATIONS**6.1 SCREENED POPULATION**

The screened population will consist of all patients who signed informed consent and received a patient identification (PID) number.

6.2 OPEN-LABEL SAFETY POPULATION

The OL safety population will consist of all patients in the screened population who took at least 1 dose of OL cariprazine during the OLTP of the study.

6.3 OPEN-LABEL INTENT-TO-TREAT POPULATION

The OL intent-to-treat (ITT) population will consist of all patients in the OL safety population who had at least 1 postbaseline assessment of the PANSS or Clinical Global Impressions–Severity (CGI-S) scores during the OLTP of the study.

6.4 OPEN-LABEL SAFETY-FOLLOW-UP POPULATION

The OL SFU population will consist of patients in the OL safety population who were not randomized and completed at least one visit in the SFU period.

6.5 RANDOMIZED POPULATION

The randomized population will consist of all patients in the OL safety population who were randomized to a treatment group in the study.

6.6 DOUBLE-BLIND SAFETY POPULATION

The DB safety population will consist of all patients in the randomized population who took at least 1 dose of DB IP.

Patients will be included in the treatment group corresponding to the DB IP they actually received regardless of the treatment they were randomized to.

6.7 DOUBLE-BLIND INTENT-TO-TREAT POPULATION

The DB ITT population will consist of all patients who took at least 1 dose of DB IP and had at least 1 post-randomization assessment of the PANSS or CGI-S scores during the DBTP of the study.

Patients will be included in the randomized treatment group for the DB ITT population.

7.0**STUDY PATIENTS****7.1****PATIENT DISPOSITION**

The OLTP starts with the first dose of OLTP and ends with one of the following: the last scheduled assessment at the Visit 13/end of OLTP (Week 18) or early termination (ET) before Visit 13 (Week 18) for patients who do not enter the DBTP; or 1 day before the first dose of DBTP (or the date of the first dose of the DB IP if the last scheduled assessment date in the OLTP is on the date of the first dose of the DBTP) for patients who enter the DBTP.

The DBTP starts with the first day of randomization and ends with the last scheduled assessment at Visit 26 (Week 44) or ET.

The SFU period starts one day after the end of the previous period and ends with the last available assessment. For patients without Visit 27 (Week 46) or Visit 28 (Week 48) assessment, the SFU period would not be derived.

Screen-failure patients (ie, patients screened but not included in the OL Safety Population) and the associated reasons for failure will be tabulated overall for the Screened Population.

The number and percentage of patients in the Screened, OL Safety and OL ITT Populations will be summarized overall and by study center. The number and percentage of patients in the Randomized, DB Safety, and DB ITT Populations will be summarized overall by treatment group and by treatment group and study center.

The number and percentage of patients in the OL Safety Population, who prematurely discontinued from the OLTP, who completed the OLTP, who entered the DBTP, and who entered the SFU period will be summarized overall and by reasons for premature discontinuation as recorded on the respective disposition pages of the electronic case report form (eCRF).

Similarly, the number and percentage of patients in the DB Safety Population who completed the DBTP, who prematurely discontinued from the DBTP, and who entered the SFU period will be summarized overall, by DB treatment group and by reasons for premature discontinuation as recorded on the respective disposition pages of the eCRF. Patients who relapse during the DBTP will also be summarized as completing the study.

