7.1.7 Double-blind Intent-to-Treat Population

The double-blind intent-to treat (DB ITT) population will consist of all patients in the DB safety population who had at least 1 post-randomization assessment of the PANSS or CGI-S scores during the DB treatment period of the study.

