Physical examination														X	
ECG														X	

Study Period	Double-blind Treatment Period												Safety Follow-up		
	14	15	16	17	18	19	20	21	22	23	24	25	26/ET	27	28 ^c
Visit Number/ Visit Title	20	22	24	26	28	30	32	34	36	38	40	42	44	46	48
End of Study Week (Day)	(141)	(155)	(169)	(183)	(197)	(211)	(225)	(239)	(253)	(267)	(281)	(295)	(309)	(323)	(337)
Visit Window (Days)	± 3	± 3	± 3	± 3	± 3	± 3	± 3	± 3	± 3	± 3	± 3	± 3	± 3	± 3	± 3
Ophthalmological examination ^c													X		(X)
AEs/SAEs	X	X	X	X	X	X	X	X	X	X	X	X	X	X	X

Note: If necessary, Visits 14 to 28 may be conducted up to 3 days before or after the scheduled visits. The visit windows for each scheduled visit are relative to Visit 13 for Visits 14 through 26/ET, and relative to Visit 26/ET for Visits 27 and 28.
 AE = adverse event; AIMS = Abnormal Involuntary Movement Scale; BACS = Brief Assessment of Cognition in Schizophrenia scale; BARS = Barnes Akathisia Rating Scale; CGI-I = Clinical Global Impression-Improvement scale; CGI-S = Clinical Global Impression-Severity scale; C-SSRS = Columbia-Suicide Severity Rating Scale; ECG = electrocardiogram; EPS = extrapyramidal symptoms; ET = early termination; IP = investigational product; SCI-PANSS = Structured Clinical Interview for the Positive and Negative Syndrome Scale; PSP = Personal and Social Performance scale; SAE = serious adverse event; SAS = Simpson-Angus Scale.

^a For women of childbearing potential only.

^b Blood pressure and pulse rate will be measured both standing and supine.

^c Every attempt should be made to complete the Visit 26/ET ophthalmological examination on the same day as all other Visit 26 procedures. Any patients with a finding of cataracts at Visit 26/ET must be scheduled for a follow-up ophthalmological examination at Visit 28. The Visit 28 ophthalmological examination is only applicable to patients with a postbaseline finding of cataracts.

5.0 **OBJECTIVES**

- 1) To evaluate the efficacy and safety of cariprazine at a target dose of 4.5 mg/d compared with placebo in prevention of relapse in patients with schizophrenia who were initially stabilized on a target dose of 4.5 mg/d;
- 2) To evaluate the efficacy and safety of cariprazine at a target dose of 3.0 mg/d compared with placebo in prevention of relapse in patients with schizophrenia who were initially stabilized on a target dose of 4.5 mg/d.

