10.0 EFFICACY ANALYSES

All efficacy analyses for the OLTP will be performed using the OL ITT population, unless stated otherwise. Baselines for efficacy parameters in the OLTP will be defined as the last non-missing efficacy assessment before the first dose of OL IP.

All efficacy analyses for the DBTP will be performed using the DB ITT population, unless stated otherwise. Baselines for the additional efficacy parameters in the DBTP will be defined as the last nonmissing efficacy assessment before the first dose of DB IP.

All statistical tests will be 2-sided hypothesis tests performed at the 5% level of significance and all confidence intervals (CIs) will be 2-sided 95% CIs, unless stated otherwise.

To accommodate the flexible duration of the OLTP, the derived visits in the DBTP will be named as Week *i* post randomization (or DB Week *i*) for a specific Week *i* after the first dose of the DB study medications. The total exposure to IPs for patients in Week *i* post randomization will vary because of the flexible OLTP. The detailed week-mapping windows is provided in Section 16.1.

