10.1 PRIMARY EFFICACY PARAMETER

The primary efficacy parameter is the time to first relapse during the DBTP, defined as the number of days from the randomization date to the first relapse date. Relapse during the DBTP will be defined as the occurrence of any of the following:

- Increase in PANSS total score by $\geq 30\%$ for patients who had a PANSS total score of ≥ 50 at Randomization/Visit 13 (Week 18) or a ≥ 10 -point increase in PANSS total score for patients who had a PANSS total score < 50 at Randomization/Visit 13 (Week 18)
- Increase in CGI-S score by 2 or more points relative to Randomization/Visit 13 (Week 18)
- Score of > 4 on 1 or more of the following 7 PANSS items: P1: delusions; P2: conceptual disorganization; P3: hallucinatory behavior; P6: suspiciousness/persecution; P7: hostility; G8: uncooperativeness; G14: poor impulse control
- Deliberate self-injury or aggressive/violent behavior

- Initiation of treatment with a mood stabilizer, antidepressant, antipsychotic agent, or with a benzodiazepine that exceeds the protocol-specified allowance or duration (ie, more than 2 mg/d of lorazepam equivalent or for more than 3 consecutive days) to treat worsening symptoms of schizophrenia or any other psychiatric disorder as judged by the clinical impression of the investigator
- Psychiatric hospitalization due to worsening of the patient's underlying condition
- Exacerbation of psychiatric illness as judged by clinical impression of the investigator (e.g., clinically significant agitation, suicidal or homicidal ideations)

Patients who did not meet the above relapse criteria will be censored at the time of completion or discontinuation from the study.

To test the primary null hypotheses that the distribution of the time to first relapse for each of the cariprazine 4.5 mg/d and 3.0 mg/d treatment groups are not different from that for the placebo treatment group, the log-rank test is used to compare the time to relapse between each cariprazine group and placebo group for the DB ITT population. Estimates of the hazard ratio and 95% CIs will be based on the Cox proportional hazards model with treatment group as explanatory variable. The Kaplan-Meier estimates for the cumulative distribution of the relapse rate for each treatment group will be provided.

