19.0 REFERENCES

National Institutes of Health, National Heart, Lung, and Blood Institute, National High Blood Pressure Education Program. The Seventh Report of the Joint National Committee on Prevention, Detection, Evaluation, and Treatment of High Blood Pressure. NIH Publication No. 04-5230, 2014

20.0**APPENDICES****APPENDIX I SAS CODE FOR PLANNED ANALYSES OF THE PRIMARY EFFICACY VARIABLE**

The primary efficacy analysis for time to relapse include (1) the log-rank test, (2) the Cox proportional hazards model with treatment group as covariate, (3) subgroup analysis. The sample SAS code for these analyses are provided below. Note in the data set adtte (DB ITT population), variables trt02pn and trt02p are for the double-blind treatment group, subgroup is for subgroups of age, gender, race, or region, aval is for the time (days) to censor/relapse, and cnsr is for the status of censored (=0) or relapse (=1).

- SAS codes for testing the primary null hypotheses that the distribution of the time to first relapse for each of the cariprazine 4.5 mg/d and 3.0 mg/d treatment groups are not different from that for the placebo treatment group using log-rank test

```
proc lifetest data=adtte atrisk plots=survival(f atrisk=0 to 200 by
10 );
  time aval*cnsr(0);
  strata trt02p/test=logrank diff=control('Placebo');
  ods output ProductLimitEstimates=outests1 HomTests=test;
run;
```

- SAS codes for estimating the hazard ratio and 95% CIs based on the Cox proportional hazards model

```
proc phreg data=adtte;
  class trt02p(ref="Placebo");
  model aval*cnsr(0)=trt02p/rl=wald;
run;
```

- SAS codes for subgroup analyses

```
proc lifetest data=adtte atrisk plots=survival(f atrisk=0 to 200 by
10 );
  by subgroup;
  time aval*cnsr(0);
  strata trt02p/test=logrank diff=control('Placebo');
run;

proc phreg data=adtte;
  by subgroup;
  class trt02p(ref="Placebo");

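### The primary relapse analysis leaves out any randomised patient without a post-randomisation PANSS or CGI-S, so a few early relapses could be lost; the expected effect is small and cheap to remove

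*SAP*

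**What the plan says.** SAP 6.7 defines DB ITT as patients who took at least one dose of double-blind study drug and "had at least 1 post-randomization assessment of the PANSS or CGI-S scores during the DBTP of the study". Protocol 7.1.7 sets the same condition: "at least 1 post-randomization assessment of the PANSS or CGI-S scores during the DB treatment period of the study".

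SAP 10.1 applies this set to the primary endpoint: "the log-rank test is used to compare the time to relapse between each cariprazine group and placebo group for the DB ITT population". The dataset note in SAP Appendix I restricts the log-rank and Cox code to DB ITT as well. SAP 10.0 adds a general rule: "All efficacy analyses for the DBTP will be performed using the DB ITT population, unless stated otherwise". The two imputation-based sensitivity analyses in SAP 10.1 and Appendix II name no other set. No analysis of relapse on all randomised patients is planned.

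The endpoint itself is "defined as the number of days from the randomization date to the first relapse date". Three of the seven criteria are scale thresholds. The other four are self-injury or violence, a newly started psychotropic or excess benzodiazepine, psychiatric hospitalisation, and an exacerbation judged by the investigator.

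**The concern.** Requiring a post-baseline rating makes sense for a change-from-baseline scale analysis. It does not suit a time-to-event endpoint that can occur without any rating. Here the clock starts at randomisation and SAP 14.0 builds the event target on all 345 randomised patients, yet membership of the analysis set depends on data collected afterwards.

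A relapse is lost only if three things coincide:

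- it occurs before the first scheduled double-blind rating at Visit 14;
- it is met only by one of the four non-rating criteria;
- no early-termination or unscheduled PANSS or CGI-S exists.

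An example is a patient hospitalised for relapse on day 8 who then withdraws consent before being rated. Protocol 8.8 makes the early-termination assessment a matter of best effort and does not expect it after withdrawal of consent. Protocol 8.8 also asks whether a loss to follow-up was related to an exacerbation. That record alone is not a relapse, so such a case is a lost event only if the investigator also judges it one.

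At stake are a little power and the principle that every randomised patient's relapse counts in the test designed around it. The rule still operates after early termination, because SAP Appendix IV keeps the primary efficacy analysis for the abbreviated report.

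**Working it through.** **Inputs from SAP 14.0.** Hazard ratio 0.50; placebo relapse 46% at Week 26; other dropout 20% at Week 26; 115 per arm; two-sided 5%; 85% power; about 103 events. Constant hazards for relapse and dropout are my assumption.

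**Rates per week.** Placebo relapse λp = −ln(0.54)/26 = 0.0237; cariprazine relapse λc = λp/2; dropout η = −ln(0.80)/26 = 0.00858.

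**Reproducing the plan.** Expected relapses per arm by time T are 115 × λ/(λ+η) × (1 − exp(−(λ+η)T)). At T = 26 weeks this gives 47.95 on placebo and 27.49 on each cariprazine arm:

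- three arms: 47.95 + 2 × 27.49 = 102.9, matching the stated 103;
- one pair: 75.44, against a Schoenfeld requirement of 75;
- power = Φ(√(75.44/4) × ln 2 − 1.96) = 85.3%.

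**Relapses before Visit 14.** SAP Table 4-2 puts Visit 14 at day 141 and Table 4-1 puts Visit 13 at day 127, so the gap is 14 days. The Table 4-2 note says "Visits 14 to 28 may be conducted up to 3 days before or after the scheduled visits", which gives 11 to 17 days. Pair totals below come from unrounded values.

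| Days after Visit 13 | Placebo | Each cariprazine arm | Pair | Share of 75.44 |
|---|---|---|---|---|
| 11 | 4.18 | 2.11 | 6.28 | 8.3% |
| 14 | 5.28 | 2.67 | 7.95 | 10.5% |
| 17 | 6.37 | 3.23 | 9.59 | 12.7% |

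A visit held later than its window would raise these figures.

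**Relapses lost.** Lost = early relapses × s × m, where s is the share met only by a non-rating criterion and m the share of those with no rating. The documents give neither. Assumed ranges are s = 25% to 75% and m = 10% to 40%, so s × m runs from 0.025 to 0.30, with a middle case of 0.50 × 0.20 = 0.10.

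| Case | Lost, 14 days | Power | Lost, 17 days | Power |
|---|---|---|---|---|
| Lowest (0.025) | 0.20 | 85.23% | 0.24 | 85.21% |
| Middle (0.10) | 0.79 | 84.95% | 0.96 | 84.87% |
| Highest (0.30) | 2.38 | 84.19% | 2.88 | 83.95% |
| Every early relapse lost | 7.95 | 81.25% | 9.59 | 80.30% |

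The middle case is 0.79/75.44 = 1.1% or 0.96/75.44 = 1.3% of pairwise events.

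**Simulation.** Exponential relapse and dropout, 182 days of follow-up, a 17-day cut-off, loss assumed equal by arm, 20,000 trials per scenario. Early dropouts without a relapse were excluded with probability m.

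| Case | Exclusion | HR | Power | Rejection under the null |
|---|---|---|---|---|
| Middle | with | 0.505 | 83.8% | 5.2% |
| Middle | without | 0.505 | 84.1% | 5.2% |
| Highest | with | 0.503 | 83.5% | 4.9% |
| Highest | without | 0.504 | 84.8% | 5.1% |

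The two runs without exclusion are the same scenario yet differ by 0.7 points of power (84.1% and 84.8%). The simulation is therefore too coarse to resolve the middle-case power loss, and the closed-form figures are the better guide there. It shows no sign of an effect on the hazard ratio or the type I error.

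**Unequal loss, for illustration.** If only placebo relapses were lost, an approximate calculation gives HR 0.511, 0.522 or 0.533 and power 82.6%, 79.6% or 76.3% for 1, 2 or 3 lost events. Nothing in the documents indicates such an imbalance.

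**Shorter follow-up.** The terminated study's event count is not given. If all follow-up were cut at 13 weeks (assumed), early relapses would be 17.9% (14 days) or 21.6% (17 days) of pairwise events. The middle case would then lose 1.8% or 2.2%.

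**The case against.** The strongest reply is that the plan is consistent and already handles nearly all such patients. Protocol and SAP agree on DB ITT, and it was prespecified. Relapse requires discontinuation (Protocol 8.9). Anyone who took study drug and stops should have a final assessment (Protocol 8.8), which includes both scales (Protocol 8.4.6) and lies inside the double-blind period (SAP 7.1). A rating on either scale is enough, and Protocol 8.6 allows unscheduled visits. The planned population counts by arm and the relapse listing would reveal anyone left out. The loss rates above are assumptions, and 40% without a final rating sits poorly with Protocol 8.8. The hazard just after randomisation may also differ from a constant one, since every patient met the response threshold at Visit 13. Finally, the study was terminated, so the 85% power target no longer governs the result.

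Most of this stands, and it is why the point is minor. It does not close the gap. The final assessment is not guaranteed, no rule retains a relapser without a rating, and counts and listings do not return the event to the test. Early termination cuts both ways: each lost relapse weighs more among fewer events, but proportionally fewer losses are expected.

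**Conclusion.** The concern holds, as a minor point and a cheap improvement rather than the repair of an error that threatens the conclusion. The primary set can omit a true primary event, and no planned analysis restores it. The likely cost is about one relapse per pairwise comparison and less than half a point of power; at the top of the assumed range it is 2.9 relapses and about 1.4 points (85.32% − 83.95%). The direction of any bias is unknown and no arm-specific loss is documented. The size rests on the plan's event rates, a constant hazard and assumed values for the unrated share. That the rule can exclude a relapse follows from the text alone.

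**What to change.** Run the primary log-rank, Cox and Kaplan-Meier analyses on the Randomized Population (SAP 6.5), by randomised arm. Count a relapse by any of the seven criteria whether or not a rating exists. Keep the existing censoring rule, "Patients who did not meet the above relapse criteria will be censored at the time of completion or discontinuation from the study", and censor at day 1 where nothing is known after randomisation. Keep DB ITT for the scale analyses and as a supportive log-rank. Report, by arm, the patients and relapses that DB ITT would exclude.

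This needs no new data and leaves the sample size and event target unchanged. It takes text changes in SAP 10.0, 10.1, the Appendix I dataset note and Appendix IV. It also needs an entry in SAP 17.0, because Protocol 7.1.7, 7.3 and 7.3.1 define DB ITT or apply it to the primary analysis. The downside is a documented departure from the protocol's primary set, including loss of the one-dose condition, and one extra run.

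The documents do not show whether treatment codes have been unblinded. If they have, leave DB ITT as the named primary set and report the all-randomised analysis as a labelled sensitivity analysis, which costs only the extra run.

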8.4.4 End of Open-label Period/Randomization Visit (Visit 13)

The following procedures will be performed at Visit 13:

- Review concomitant medications
- Collect vital signs measurements, including weight
- Measure waist circumference
- Administer SCI-PANSS and CGI-S to determine whether randomization criteria (Section 4.6) have been met
 - Eligible patients: Access IWRS to randomize patient and dispense DB IP
 - Patients who do not meet randomization criteria are to undergo procedures as for Visit 26/ET and scheduled to return for the SFU Visits (Visit 27 and Visit 28)
- Assess C-SSRS, BACS, CGI-I, and PSP

- Evaluate EPS symptoms (AIMS/BARS/SAS)
- Perform ECG
- Perform ophthalmological examination. NOTE: For patients eligible for randomization, every attempt should be made to complete the Visit 13 ophthalmological examination on the same day as all other Visit 13 procedures. If the examination cannot be accommodated, it must occur within 7 days after randomization.
- Collect samples for UDS; assess blood alcohol concentration via breathalyzer
- Collect blood samples for clinical laboratory determinations
- Collect blood samples for serum pregnancy test (women of childbearing potential only)
- Collect blood sample for hemoglobin A1c
- Review and assess AEs and SAEs
- Collect IP blister cards and perform IP compliance and accountability
- Access IWRS to dispense IP

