16.0 DATA HANDLING CONVENTIONS

16.1 VISIT TIME WINDOWS

Table 16-1 presents the visits assigned for efficacy and safety analyses and the corresponding range of treatment days (window) during which an actual visit may occur.

Table 16-1 Visit Time Windows

Derived Visit	Open-label Period	
	Scheduled Visit Day Relative to the first dose of OL IP	Window
OL Baseline	Day 1	Days \leq 1
OL Week 1	Day 8	Days [2, 11]
OL Week 2	Day 15	Days [12, 18]
OL Week 3	Day 22	Days [19, 25]
OL Week 4	Day 29	Days [26, 35]
OL Week 6	Day 43	Days [36, 49]
OL Week 8	Day 57	Days [50, 63]
OL Week 10	Day 71	Days [64, 77]
OL Week 12	Day 85	Days [78, 91]
OL Week 14	Day 99	Days [92, 105]
OL Week 16	Day 113	Days [106, 119]
OL Week 18	Day 127	120 \leq days \leq the day of the last visit during the OL period*
End of the OL Period ^a	Last Assessment during the OL	
Double-blind Period		
	Scheduled Visit Day Relative to the first dose of DB IP	Window
	Day 1	Days \leq 1
DB Baseline (for efficacy endpoints only)	Day 15	Days [2, 21]
DB Week 2	Day 29	Days [22, 35]
DB Week 4	Day 43	Days [36, 49]
DB Week 6	Day 57	Days [50, 63]
DB Week 8	Day 71	Days [64, 77]
DB Week 10	Day 85	Days [78, 91]
DB Week 12	Day 99	Days [92, 105]
DB Week 14	Day 113	Days [106, 119]

Derived Visit	Open-label Period	
	Scheduled Visit Day Relative to the first dose of OL IP	Window
DB Week 18	Day 127	Days [120, 133]
DB Week 20	Day 141	Days [134, 147]
DB Week 22	Day 155	Days [148, 161]
DB Week 24	Day 169	Days [162, 175]
DB Week 26	Day 183	176 ≤ days ≤ the day of the last visit during the DB period
End of the DB period^a	Final or Termination Visit during the double-blind treatment period	
	Safety-follow-up (SFU) Period^b	
	Scheduled Visit Day Relative to the start of SFU	Window
SFU Week 2 ^b	Day 15	+1 ≤ days ≤ 21
SFU Week 4 ^b	Final or Termination Visit of the study after day 21 .	

OL Day 1 = the date of the first dose of open-label investigational product;

DB Day 1 = the date of the first dose of double-blind investigational product. There is no Day 0.

a Presented in analysis tables for safety parameters, including but not limited to electrocardiograms, clinical laboratory values, and vital signs.

b Presented in analysis tables for vital signs.

OL = Open Label; DB = Double-blind; SFU = Safety Follow-up; ET = Early Termination; IP = Investigational Products.

* All the available OL week 18/visit 13 Ophthalmological examination will be mapped to the OL safety period.

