16.3 REPEATED OR UNSCHEDULED ASSESSMENTS OF SAFETY PARAMETERS

If a patient has repeated assessments before the start of OLTP, the results from the final non-missing assessment made before the start of the OL IP will be used as OL baseline. If end-of-study assessments are repeated or if unscheduled visits occur, the last non-missing postbaseline assessment will be used as the end-of-study assessment for generating summary statistics. However, all postbaseline assessments will be used for PCS value determinations, and all assessments will be presented in the data listings.

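### SAP 7.1 lets the open-label and double-blind periods share the randomisation day, so findings made before any double-blind dose can enter by-arm AE and worst-value safety tables

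*SAP*

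**What the plan says.** SAP 7.1 defines the periods with two different anchors. The double-blind treatment period (DBTP) is tied to randomisation: "The DBTP starts with the first day of randomization". For patients who go on to the DBTP, the end of the OLTP is tied to dosing. The default end is "1 day before the first dose of DBTP". A bracketed exception covers patients whose final open-label assessment and first DB dose share a date; for them the OLTP runs through that dose date.

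Protocol 8.4.4 makes Visit 13 both the last open-label visit and the randomisation visit, with DB product dispensed there. It allows one procedure to slip: for the eye examination, "If the examination cannot be accommodated, it must occur within 7 days after randomization".

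Elsewhere the SAP anchors DB data to the first DB dose. This holds for DB concomitant medication (8.0), DB exposure (9.1), the Hy's Law summary (11.2) and the visit windows in 16.1, where "DB Day 1 = the date of the first dose of double-blind investigational product". A footnote to Table 16-1 adds: "All the available OL week 18/visit 13 Ophthalmological examination will be mapped to the OL safety period".

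SAP 11.1 defines a TEAE from the first open-label dose and then tabulates TEAEs in the DBTP by treatment group. It has no separate DB-emergent definition and no rule for an event on a date that both periods contain. SAP 11.0 takes the last value before the first open-label dose as the safety baseline, so a Visit 13 value counts as post-baseline.

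**The concern.** Visit 13 laboratory results, and a C-SSRS that looks back to the previous open-label visit, describe the patient on open-label cariprazine. So does an AE dated to that visit but before any DB capsule. If the date also belongs to the DBTP, these findings can appear in a by-arm table as though they arose on placebo, 3.0 mg/d or 4.5 mg/d, and again in the open-label table.

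The by-arm safety tables are where the two doses are compared for tolerability. Protocol section 1 plans that comparison if both doses prove effective. Because the text does not settle the point, whoever programs the tables must choose a rule, possibly after unblinding.

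**Working it through.** The plan gives no figure for this, so the check applies its date rules.

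**Inputs**
- v = Visit 13 date, r = randomisation date, f = first DB dose date. Protocol 8.4.4 gives v = r in the normal flow. Scheduled Day 127 is used as the example.
- DBTP start = r (SAP 7.1).
- OLTP end E = f if v = f, otherwise f − 1 (SAP 7.1).
- DB Day 1 = f, there is no Day 0, and the first post-baseline DB window is Days 2 to 21 (SAP Table 16-1).

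**Formula:** shared days = max(0, E − r + 1).

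| v | r | f | E | Shared days | Visit 13 in DBTP by date | Visit 13 as DB day |
|---|---|---|---|---|---|---|
| 127 | 127 | 127 | 127 | 1 | yes | 1 |
| 127 | 127 | 128 | 127 | 1 | yes | −1 |
| 127 | 127 | 129 | 128 | 2 | yes | −2 |
| 127 | 127 | 130 | 129 | 3 | yes | −3 |
| 127 | 128 | 128 | 127 | 0 | no | −1 |
| 127 | 128 | 129 | 128 | 1 | no | −2 |

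Whenever v = r, Visit 13 lies in both periods. If randomisation falls after the Visit 13 date, Visit 13 lies only in the OLTP, and there is no shared day if the first DB dose is also on the randomisation date.

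**Which outputs are exposed**
- *By-visit DB safety tables:* not exposed. The DB day of Visit 13 is 1 or lower in every row, so it enters no post-baseline window, and the DB Baseline row is for efficacy only.
- *AE tables:* exposed. They depend on period membership by onset date.
- *Laboratory PCS:* exposed. SAP 11.2 counts any PCS value in the corresponding period. The denominator is exposed too: a patient with no laboratory test after the first DB dose still qualifies through Visit 13.
- *C-SSRS worst category:* exposed, because it is summarised by period.
- *Ocular events:* the Table 16-1 footnote assigns the examination to open label but says nothing about an AE dated to it.

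**Size**
- Time: 1 shared day / 182 days (26 weeks) = 0.55%.
- Scheduled assessments per completer, without and with Visit 13: laboratory 3 and 4 (Visits 18, 22, 26, plus 13; Protocol 6.5.3); C-SSRS 13 and 14 (Visits 14 to 26, plus 13; Protocol 6.5.8.2).
- Laboratory PCS rate, *assuming* an independent probability q per assessment, compares 1 − (1 − q)^3 with 1 − (1 − q)^4. For q = 1%: 2.97% and 3.94%. For q = 5%: 14.26% and 18.55%.
- Between-arm contrast, *assuming* true DB rates of 10% and 5% and an independent Visit 13 rate p in both arms:
  - p = 1%: 1 − 0.90 × 0.99 = 10.9%; 1 − 0.95 × 0.99 = 5.95%. The ratio goes from 2.0 to 1.83 and the difference from 5 to 4.95 points.
  - p = 5%: 1 − 0.90 × 0.95 = 14.5%; 1 − 0.95 × 0.95 = 9.75%. The ratio goes from 2.0 to 1.49 and the difference from 5 to 4.75 points.

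**The case against.** The best reply is that Visit 13 is plainly meant to be open-label. The schedules title it as the end of that period, Protocol 8.4.5 starts the DB visits at Visit 14, and the same-day clause in SAP 7.1 exists to keep a final assessment in the OLTP. This is good evidence of intent for scheduled assessments. It does not remove Visit 13 from a DBTP that is defined by date, and it gives no help with AEs, which carry dates and not visit numbers.

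Other limits stand in full:
- A reader might infer that all Visit 13 findings are tabulated by DB arm. Table 16-1 rules that out for by-visit tables.
- A reader might take "all postbaseline assessments will be used for PCS value determinations" (SAP 16.3) as placing Visit 13 in the DBTP. That sentence concerns repeated and unscheduled assessments; the exposure comes from 7.1 together with the open-label baseline.
- ECG PCS, EPS-scale and hypertension-shift tables would be exposed under the full plan, but Appendix IV does not list them for the abbreviated report.
- Open-label and DB tables have separate denominators, so no patient is counted twice within one table.
- A same-day AE that follows the first DB capsule may be a true DB event.
- An ocular event dated several days after randomisation may follow DB dosing, so counting it in the DB table by onset date is defensible. The examination footnote does not justify moving all such events to open label.

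**Conclusion.** The period definitions conflict and should be corrected, but the scope is limited. Under the protocol's visit flow the periods share at least the randomisation day, and no stated rule decides where a finding made on it before any DB dose belongs. Under early termination the affected outputs are the DBTP summaries of TEAEs, TESAEs, ocular events, laboratory PCS and C-SSRS.

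Three stronger conclusions are tempting and are not supported. The overlap is not universal, as the fifth row of the table shows. The efficacy result is not touched, because time to relapse runs from randomisation and Visit 13 scores are the intended DB baseline. Nor is there a general pull of safety contrasts toward no difference: a roughly equal addition to each arm lowers ratios but leaves risk differences nearly unchanged, and the safety analyses are descriptive.

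The real size cannot be stated, since the documents give no Visit 13 event rates. The percentages above rest on assumed rates and on independence between assessments; abnormalities that persist from Visit 13 into the DB period would make the effect smaller. The conclusion also assumes that the tables are programmed from SAP 7.1 as written.

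**What to change.** Amend SAP 7.1 for safety summaries only:
1. Start the DBTP at the first DB dose, in line with SAP 8.0, the Hy's Law rule in 11.2, and Table 16-1.
2. Assign Visit 13 laboratory, ECG, vital-sign, EPS and C-SSRS assessments to the OLTP only.
3. Assign an AE with onset on the first-DB-dose date to the OLTP unless a recorded onset time is after that dose. Step 1 alone is not enough: when the first dose is on the Visit 13 date, both periods would still contain that date.
4. Assign ocular AESIs by onset date against the first DB dose, with the same same-day rule. Flag those first found at a delayed Visit 13 eye examination; do not move them to the OLTP.

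Keep the randomisation date as time zero for time to relapse.

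The cost is a few lines of SAP text and one programming flag. The downside is small: an event that began hours after the first DB dose, with no recorded time, goes to the open-label table.
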